8.1.2 Data Sets Analyzed

The full analysis set is comprised of all enrolled subjects who took at least one dose of the study drug and subjects will be analyzed in the treatment regimen to which she was assigned. For the Open-label Run-in period (through Treatment Month 3) of the study, all subjects who receive at least 1 dose of study drug during the Open-label Run-in period will be included in the Open-label full analyses. For the Double-blind Period of the study (Months 4 – 24), all subjects who receive at least 1 dose of study drug during the Double-blind Period will be included in the Double-blind full analyses. The full analysis set will be used for all analyses unless otherwise specified in the SAP.

8.1.3 Demographic, Baseline Characteristics and Concomitant Medications

Demographic and baseline characteristics will be summarized by treatment groups as well as the following two groups:

- Subjects discontinued prior to the Double-blind Period.
- Subjects treated in the Double-blind Period.

Medical history, protocol deviations, premature discontinuations, concomitant medications, and study drug exposure will be summarized. No treatment group comparisons will be made. Unless noted otherwise, the baseline values will be defined as the last value obtained prior to the first dose of the study drug during the Open-label Run-in Period.

8.1.4 Efficacy

8.1.4.1 General Considerations

Analysis details for Months 1 through 24 of the Treatment Period will be specified in the SAP.

The primary efficacy comparisons will be at Treatment Month 6 between the Elagolix 200 mg BID plus E2/NETA treatment group (Group C) and elagolix 150 mg QD group (treatment Group B) in patients who are incomplete responders to elagolix 150 mg QD treatment at Month 3.

For efficacy data collected during Month 7 – 24 of the treatment period, summaries will be provided for the following treatment groups.

- Efficacy responders to elagolix 150 mg QD at Month 3 and continue treatment through Month 24 (Group A).
- Incomplete efficacy responders to elagolix 150 mg QD at Month 3 and randomized to elagolix 200 mg BID plus E2/NETA 1 mg/0.5 mg QD treatment group and continue treatment through Month 24 (Group C).
- Incomplete efficacy responders to elagolix 150 mg QD at Month 3, randomized to elagolix 150 mg QD treatment group and remain incomplete efficacy responders at Month 6, dose increased to elagolix 200 mg BID plus E2/NETA 1 mg/0.5 mg QD through Month 24 (Group D).
- Incomplete efficacy responders to elagolix 150 mg QD at Month 3, randomized to elagolix 150 mg QD treatment group and are efficacy responders at Month 6 continue treatment through Month 24 (Group E).

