Subjects assessed as "efficacy responders" (as defined above) will be assigned to continue dosing with elagolix 150 mg QD (Group A) in a blinded manner via Interactive Response Technology (IRT). All other subjects assessed as "incomplete efficacy responders" will be assigned randomly (in an equal ratio) via IRT to either elagolix 150 mg QD (Group B) or elagolix 200 mg BID plus E2/NETA (1 mg/0.5 mg) QD (Group C) for 3 months. To preserve the blind, IRT will be utilized for study drug assignment for all subjects. The first dose from the newly assigned study drug kit at Treatment Month 3 will be administered at the site. The pharmacokinetic and pharmacodynamics samples must be obtained prior to study drug administration at the Treatment Month 3 visit.

At the Treatment Month 6 study visit, in a blinded manner via IRT, all subjects who were incomplete efficacy responders and randomly assigned at Treatment Month 3 to elagolix 150 mg QD will again be assessed for efficacy response in the same manner as was done at the Treatment Month 3 visit. All subjects in this group (Group B) who become efficacy responders will continue dosing with elagolix 150 mg QD in a blinded manner (Group E). All other subjects in this group who are assessed as incomplete efficacy responders at Month 6 will escalate dosing to elagolix 200 mg BID plus E2/NETA (1 mg/0.5 mg) QD (Group D). To preserve the blind, IRT will be utilized for treatment assignment of all subjects; however, only subjects randomly assigned at Treatment Month 3 to the elagolix 150 mg QD (Group B) will have a chance for dose modification. The first dose from the newly assigned study drug kit at Treatment Month 6 will be administered at the site. The pharmacokinetic and pharmacodynamics samples must be obtained prior to study drug administration at the Month 6 visit.

At the Treatment Month 6 study visit, any subjects that have zero entries for the Daily Diary for endometriosis-associated pain score via NRS during the 35 day window prior to the study visit will continue dosing on the current dose assignment for the remainder of the treatment period.

The treatment assignments following the Treatment Month 6 study visit will continue for all subjects for the duration of the 24-month Treatment Period in a blinded manner. There will not be further dose adjustments following the Treatment Month 6 visit for any subject.

BMD Assessment and Subject Specific Safety Stopping Criteria for BMD During the Treatment Period:

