8.1.4.3 Secondary Efficacy Variables

Key Secondary Efficacy Endpoints

The following key secondary efficacy endpoints based on data collected during the first 6 months of the treatment period will be summarized by treatment regimen:

- Change from baseline in DYS
- Change from baseline in NMPP
- Change from baseline in dyspareunia
- Change from baseline in Daily Diary endometriosis-associated pain score via NRS
- Change from baseline in rescue analgesic use across both classes of rescue analgesics based on average pill counts
- Percentage of subjects with 30% or more reduction from baseline based on the 35 day mean of the Daily Diary endometriosis-associated pain score via NRS

Additional details regarding the key secondary efficacy endpoints will be provided in the SAP.

Additional Secondary Efficacy Endpoints

Additional secondary efficacy endpoints based on data collected during the first 6 months of the treatment period will include the following.

- Proportion of responders as assessed by change and percent change from Baseline in average pain score and rescue analgesic use monthly for DYS, NMPP, dyspareunia, and Daily Diary endometriosis-associated pain score via NRS, respectively.
- Proportion of responders as assessed by change and percent change from Baseline in average pain score alone (i.e., not taking into consideration of analgesic use) monthly for DYS, NMPP, dyspareunia, and Daily Diary endometriosis-associated pain score via NRS respectively.
- Change and percent change from Baseline, in the monthly average pain score (DYS, NMPP, dyspareunia), and Daily Diary endometriosis-associated pain score via NRS.
- Change from Baseline in rescue analgesic use (average pill counts) to treat endometriosis-related pain, as assessed using information from the e-Diary.
- Proportion of analgesic use responders monthly (based only on reduction of rescue analgesics used).

Additional secondary efficacy endpoints during the 24 months treatment period will include the following.

- Patient Global Impression of Change (PGIC).
- Monthly site administered overall endometriosis-associated pain questionnaire (7-day recall).
- Patient reported outcome (PRO) and outcomes Rating Scales questionnaires.

Summaries for Secondary Efficacy Variables

Unless otherwise specified, no statistical tests will be performed for secondary efficacy endpoints.

Analysis details will be specified in the SAP.

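### Months 7–24 efficacy summaries show Group B only as its Month 6 responders and non-responders, so the randomized long-term contrast with Group C is omitted

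*Combined protocol and SAP*

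**What the plan says.** Women who are incomplete responders at Month 3 are randomized 1:1 to Group B (150 mg QD) or Group C (200 mg BID plus E2/NETA). At Month 6, Section 5.1 states that "only subjects randomly assigned at Treatment Month 3 to the elagolix 150 mg QD (Group B) will have a chance for dose modification". Group B women are then sorted on the daily pain NRS into D (incomplete responders, escalated) and E (responders, continued). Group C is assessed too but is never divided.

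For Months 7–24 efficacy, Section 8.1.4.1 states that "summaries will be provided for the following treatment groups": A, C, D and E. Both halves of Group B are defined by what happened at Month 6. D are those who "remain incomplete efficacy responders at Month 6, dose increased to elagolix 200 mg BID plus E2/NETA 1 mg/0.5 mg QD through Month 24 (Group D"), and E are those who "are efficacy responders at Month 6 continue treatment through Month 24 (Group E"). No summary of Group B as randomized is listed for this period.

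Four other statements bear on the point:

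- The randomized comparison that is planned is B versus C at Month 6 ("The primary efficacy comparisons will be at Treatment Month 6 between the Elagolix 200 mg BID plus E2/NETA treatment group (Group C") versus Group B). Month 6 is also the only efficacy time point in the objectives (Section 4.0).
- Section 8.1.4.3 lists PGIC, the 7-day-recall pain NRS and the PRO questionnaires as 24-month outcomes, and adds: "Unless otherwise specified, no statistical tests will be performed for secondary efficacy endpoints".
- Section 8.1.2 says that "subjects will be analyzed in the treatment regimen to which she was assigned". Section 5.5.1 has the IRT assign every woman again at Month 6, so this sentence does not settle whether Group B women are reported by their Month 3 or their Month 6 assignment.
- Section 8.1.4.1 opens with a deferral: "Analysis details for Months 1 through 24 of the Treatment Period will be specified in the SAP". The text supplied contains no separate SAP.

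**The concern.** Group C enters Months 7–24 with its good and poor Month 6 responders together. Group B enters as two tables, one holding only its poor responders and one only its good ones. C beside D, or C beside E, is an unselected arm beside an arm selected on a post-randomization outcome. The outcome used for selection (daily endometriosis pain) is closely related to those summarized afterwards (7-day pain, PGIC, PROs), so some of the Month 6 difference should carry forward whatever the treatment does.

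Section 5.1 describes a study of efficacy over 24 months, and Section 3.3 says that it should inform dosing and escalation in incomplete responders. A prescriber will ask whether escalating at Month 3 does better in the long run than staying on 150 mg and escalating at Month 6 only if needed. Randomization protects exactly that contrast (C versus all of B), and the listed groups do not show it.

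The listed groups also leave some women without a row. Under Section 5.1, a Group B woman with no NRS entries in the 35 days before Month 6 stays on her current dose, so she is never classed as responder or incomplete responder and meets neither the D nor the E definition. A Group C woman in the same position remains in C.

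**Working it through.** **Inputs.** From Section 8.3: 890 enrolled, 50% responders at Month 3, 1:1 randomization, Month 6 co-primary response of 20% (B) and 50% (C), 80% of Group B switched at Month 6, 25% completion. Assumed here, with no source in the documents: the correlation between Month 6 and later scores, a common later response rate of 20%, and equal completion across groups.

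**1. Reproducing the plan's figures.**

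- Randomized: 890 × 0.5 = 445, so 445 / 2 = 222.5 per arm.
- Power at 222 per arm, normal approximation: null SE = √(2 × 0.35 × 0.65 / 222) = 0.0453; alternative SE = √((0.20 × 0.80 + 0.50 × 0.50) / 222) = 0.0430; z = (0.30 − 1.96 × 0.0453) / 0.0430 ≈ 4.9. Power is above 99.9%, in line with the stated figure of more than 90%.
- 150 mg completers: (445 + 222.5 × 0.20) × 0.25 = 489.5 × 0.25 = 122.4, which agrees with at least 120 if nobody is lost before Month 3.

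**2. Size of the groups.** Before dropout, C = 222.5, D = 222.5 × 0.80 = 178 and E = 222.5 × 0.20 = 44.5. At 25% completion these become about 55.6, 44.5 and 11.1 at Month 24.

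**3. What selection alone would do.** Suppose B and C are identical in every respect, before and after Month 6. Take the Month 6 score as standard normal with higher meaning better, and let the top 20% be E. The cut-off is z = 0.842, where the normal density is 0.280.

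- Mean Month 6 score in E: 0.280 / 0.20 = +1.40 SD.
- Mean Month 6 score in D: −0.280 / 0.80 = −0.35 SD.
- Mean in C: 0.

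A later score with correlation r to the Month 6 score carries forward r times these means:

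| r (assumed) | E minus C | D minus C | D and E pooled minus C |
|---|---|---|---|
| 0.4 | +0.56 SD | −0.14 SD | 0 |
| 0.6 | +0.84 SD | −0.21 SD | 0 |
| 0.8 | +1.12 SD | −0.28 SD | 0 |

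The pooled column is zero because 0.20 × 1.40 − 0.80 × 0.35 = 0.

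On a responder scale, a simulation with a true later response of 20% in both arms gave E 44%, D 14% and C 20% at a correlation of 0.5. At 0.3 it gave 33%, 17% and 20%; at 0.9, 75%, 6% and 20%. Pooled D and E matched C each time.

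**4. Precision of the omitted contrast.** For a 50% response rate, the 95% half-width for B versus C is 1.96 × √(2 × 0.25 / n). With n = 222.5 this is 0.093, about 9 percentage points. With n = 55.6 (Month 24 completers) it is 0.186, about 19 points.

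**The case against.** The strongest reply is that nothing planned is biased. The one efficacy comparison in the objectives is B versus C at Month 6; it uses the randomized groups and has ample power. Months 7–24 are untested summaries, no C versus D or C versus E comparison appears anywhere, and the group definitions already state the Month 6 selection. Reporting D and E separately serves a stated purpose, because Section 8.3 counts A and E as the 24-month 150 mg population. Details are deferred to the SAP, which could add the pooled group.

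Most of that stands, and it limits the point. A reader might infer that the randomized comparison has been lost. It has not: the Month 3 assignment is held in the IRT, and pooling D, E and any Group B woman in neither restores the contrast. A reader might also infer that any C, D and E differences would be selection and nothing else. The documents do not support that either, since E stays on 150 mg and D starts the higher regimen three months after C. A real advantage for Group C's regimen could shrink or reverse the apparent lead of E. Nor can it be said that no pooled summary will ever be produced, only that the protocol text does not list one.

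What the reply does not remove is that adjacent columns will be compared whether or not a test is planned, and that the contrast randomization protects is absent from the listed set.

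**Conclusion.** The point holds as an omission and a risk of misreading, not as a flaw in the primary analysis. The Months 7–24 efficacy summaries place an unselected randomized arm beside the two outcome-selected halves of the other and do not list that other arm whole.

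The selection component alone could be about 0.56 to 1.12 SD in favour of E and 0.14 to 0.28 SD against D, relative to C. Those figures rest on identical regimens, normal scores, the protocol's 80/20 planning split and an assumed correlation of 0.4 to 0.8. They illustrate the size of the distortion and do not predict the results, and one correlation for both halves is a simplification because D changes regimen at Month 6.

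The restored contrast has limits of its own. By planning assumption, about 80% of Group B will be on Group C's regimen after Month 6, so it compares two strategies rather than two doses. If completion is 25% in both arms, about 56 per arm reach Month 24, and dropout could bias even a randomized comparison. This is a worthwhile, inexpensive improvement.

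**What to change.** In Section 8.1.4.1 and in the SAP:

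1. Keep the A, C, D and E summaries. State beside them that A, D and E are selected on response, that C contains both Month 6 responders and non-responders, and that the columns are not for comparison with one another.
2. Add a descriptive summary of Group B as randomized at Month 3 (D, E and any Group B woman in neither) versus Group C, in the Double-blind full analysis set. Give differences and 95% confidence intervals for PGIC, the 7-day-recall NRS and the PROs, at the Months 7–24 visits where Appendix C collects each. No test is needed.
3. State its interpretation: immediate escalation versus 150 mg first with escalation dependent on Month 6 response.
4. Say where Group B women with no Month 6 classification are reported, show the number contributing per arm at each visit, and say how missing data are handled.

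This needs no new data or visits and no change to the primary analysis. The cost is additional table output across several outcomes and visits, one rule for unclassified Group B women, and late estimates that must be presented as imprecise and open to dropout bias.

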8.1.4.2 Primary Efficacy Variable

8.1.4.2.1 Primary Analysis

The primary analysis of the co-primary endpoints will be performed using the Double-blind full analysis set.

The co-primary efficacy endpoints will be the proportion of responders at Month 6 based upon the mutually-exclusive scales for daily assessment of DYS and NMPP measured by the 4 point Endometriosis Daily Pain Impact Diary using the daily e-Diary.

For each of the co-primary endpoints, the criterion for defining a subject as a responder at Month 6 of the Treatment Period will include a reduction of X or greater from baseline in the average pain score as well as no increased analgesic rescue use for endometriosis-associated pain.

The subjects will record use of these rescue analgesic medications on a daily basis in the e-Diary for the first 6 months of the treatment period.

The definition of increased analgesic use is as follows:

- For the primary endpoints of DYS and NMPP, subjects will be considered non-responders if they have a 15% or greater increase from baseline in average pill count of rescue analgesics (endometriosis-associated) as further specified in [Appendix H](#).

For the first 6 months, the rescue analgesic use for any defined period will be based on the average pill count during the analysis window for each class of rescue analgesics: NSAIDs, opioids, and any (NSAIDs and/or opioids). The total pill count for each class of rescue analgesic is the sum of the pill count of the corresponding class of rescue analgesic, as reported in the e-Diary during the time period of interest. For the purposes of the rescue analgesic analysis, the number of pills within each class of rescue analgesic (NSAID or opioid) will be considered equivalent, regardless of specific pill choice,

e.g., average NSAID pill count will consider all types of NSAIDs specified in [Table 3](#) and will not be conducted separately by NSAID type.

For both DYS and NMPP, responses of "None," "Mild," "Moderate," and "Severe" will be assigned a score of 0, 1, 2, and 3, respectively.

The average pain score for DYS or NMPP for Month 6 will be based on a 35 day window. If a subject's mean score for dysmenorrhea is undefined numerically for a time point because her daily e-Diary reports indicate she did not experience her period on any days during the 35 calendar day time period, then mean score for DYS for that time point will be set equal to zero (which reflects the absence of any dysmenorrhea during that reporting time period).

For each of the co-primary endpoints, the criterion for defining a subject as a pain responder at Month 6 will be a reduction of X or greater from baseline. The threshold for response in the responder analysis (i.e., the value of X) will be chosen to represent a clinically meaningful reduction in pain. The threshold will be determined based on a ROC analysis using the PGIC at Month 6 as an anchor and change from baseline at Month 6. The PGIC is a 7-point response scale: "Since I started taking the study medication, my endometriosis related pain has: very much improved (1), much improved (2), minimally improved (3), not changed (4), minimally worse (5), much worse (6), very much worse (7)."

The responses of "much improved" and "very much improved" on PGIC will be used to define responders, and the threshold for response (the value of X) will be chosen to balance sensitivity and specificity. That is, it will be the value that corresponds to the point on the ROC curve that is closest to the upper left corner when plotting 1-specificity versus sensitivity, i.e., closest to 100% sensitivity and 100% specificity. No other covariates will be included in the ROC analysis.

The ROC analysis may identify different response thresholds for DYS and NMPP. The results of the ROC analysis, containing the determined thresholds, will be included in the final SAP prior to blind break.

The primary analysis of the co-primary endpoints will be based on a logistic regression model including treatment as the main factor and baseline pain score as a covariate to compare the proportion of responders at Month 6 between the incomplete responder groups that were randomized at Month 3 to either the elagolix 200 mg BID plus E2/NETA treatment group (Group C) or elagolix 150 mg QD group (Group B).

The primary analysis will be repeated where the responder/non-responder categorization will use percent change from baseline in pain reduction. ROC thresholds based on percent change from baseline in the average pain score will be conducted in the same manner as for the change from baseline.

Full details regarding the ROC analysis will be provided in the SAP.

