of study drug will be administered at the study site on Day 1 and study drug kits will be dispensed to subjects to continue daily dosing. Monthly on-site study visits will be conducted during the first 6 months of the Treatment Period. Subjects will be expected to come in to the site every other month during Treatment Months 7 – 12 and every third month during Treatment Months 13 – 24. Telephone contacts will be conducted at months without an on-site visit. Subjects will be asked to complete various patient-reported outcome (PRO) questionnaires at designated study visits. At the Day 1 visit (prior to dosing) and at all monthly visits (on-site and telephone contacts), site staff will administer to subjects the overall endometriosis-associated pain questionnaire, an 11-point NRS with a 7-day recall period. Starting at Treatment Month 1 and at all on-site study visits thereafter, subjects will complete the Patient Global Impression of Change (PGIC) questionnaire. Pregnancy (serum and/or urine) tests will be performed at each visit throughout the Treatment Period. Urine pregnancy test kits will be provided to subjects for use at home for the study visits when subjects are not required to come into the clinic/site. Subjects will self-administer the tests and report the results to the site at the telephone contact visits. A positive urine pregnancy test result (including those from home pregnancy testing) must be confirmed with a serum pregnancy test. If a serum pregnancy test result is positive at any time during the Treatment Period, study drug will be discontinued.

Subjects will continue to use the daily e-Diary to record DYS, NMPP; dyspareunia; Daily Diary endometriosis-associated pain score via NRS; rescue analgesic use for endometriosis-associated pain and the presence and intensity of uterine bleeding through Treatment Month 6. Throughout the 24-month Treatment Period, all subjects will continue to be allowed to take protocol specified rescue analgesic medication for endometriosis-associated pain. Use of non-protocol specific analgesic or prophylactic analgesic medications for endometriosis-associated pain will not be allowed. Subjects will record the use of protocol specific analgesic rescue medications for endometriosis-associated pain in the daily e-Diary until Treatment Month 6; thereafter, use of protocol specific analgesic rescue medications will be assessed and documented at the study visits.

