At designated study visits during the 24-month Treatment Period, blood samples will be collected for clinical safety labs, including vitamin D levels. In addition, blood samples will be collected for assay of serum estradiol, plasma concentrations of elagolix and norethindrone.

BMD will be assessed throughout the Treatment Period. Following baseline, DXA scans will be obtained at Treatment Months 6, 12, 18 and 24. A DXA scan will be required if a subject discontinues at the time of or after the Treatment Month 6 visit or if the reason for premature discontinuation is due to the occurrence of a fracture or any newly diagnosed bone condition.

Vital signs assessments will be conducted at all on-site study visits. Additional safety assessments are completed as appropriate at designated study visits throughout the Treatment Period. Adverse event and concomitant medication review will be conducted at all Treatment Period study visits.

Criteria for Assessment of Subject Status Following the Open-Label Run-In Period:

At the Treatment Month 3 study visit, subjects will be assessed as either an 'efficacy responder' or an 'incomplete efficacy responder' based on responses entered in the e-Diary on the Daily Diary endometriosis-associated pain score via NRS. The status of a subject will be determined within the e-Diary system as follows:

- Efficacy responder: $\geq 30\%$ decrease (improvement) from Baseline based on the average of the Daily Diary for endometriosis-associated pain score via NRS over a 35 day window
- Incomplete efficacy responder: $< 30\%$ decrease (improvement) from Baseline based on the average of the Daily Diary for endometriosis-associated pain score via NRS over a 35 day window
- Following conclusion of the Open-Label Run-In Period, treatment arm assignment for all subjects will become and remain blinded for the remainder of the 24-month Treatment Period. The assessment of responder status is also blinded.

At the Treatment Month 3 study visit, any subjects that have zero entries for the Daily Diary for endometriosis-associated pain score via NRS during the 35 day window prior to the study visit will continue dosing with 150 mg QD for the remainder of the treatment period (will be assigned to Group A).

Dose Escalation During the Treatment Period:

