At the Treatment Month 3 visit (i.e., the end of the Open-Label Run-In Period), in a blinded manner, the efficacy response for a subject will be assessed via the Daily Diary endometriosis-associated pain score via NRS. Subjects assessed as "efficacy responders" will continue dosing in Treatment Group A in a blinded manner for the remainder of the Treatment Period. All other subjects (assessed as "incomplete efficacy responders") will be assigned randomly (in an equal ratio) via IRT in a blinded manner to either Treatment Group B or Treatment Group C for 3 months. During the IRT randomization contact session, a unique randomization number and study drug kit number will be assigned by the IRT according to a randomization schedule generated by the Statistics department at AbbVie. However, the randomization number will not be provided to the site and is strictly used within the system for treatment assignment. At the Treatment Month 6 study visit, in a blinded manner, subjects will again be assessed for efficacy response via the Daily Diary endometriosis-associated pain score via NRS in a similar manner as was done

at the Treatment Month 3 visit. All Month 3 "incomplete efficacy responders" that were randomly assigned to be on Treatment Group B who become "efficacy responders" will continue dosing in Treatment Group E in a blinded manner. All other Month 3 'incomplete efficacy responder' subjects on Treatment Group B who are assessed as 'incomplete efficacy responders' at Month 6 will escalate dosing to Treatment Group D. To preserve the blind, at Month 6, IRT will be utilized for treatment assignment of all subjects; however, only Month 3 'incomplete efficacy responder' subjects on Treatment Group B for the additional 12 weeks after Treatment Month 3 will have a chance for dose modification. The subject number assigned via IRT at Washout of Screening does not change throughout the study.

The treatment assignments following the Treatment Month 6 study visit will continue for all subjects for the duration of the Treatment Period in a blinded manner. There will not be further dose adjustments following the Treatment Month 6 visit for any subject.

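### The primary model omits the Month 3 pain score known at randomization: no bias results, but a modest, cheap gain in precision is left unused

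*Combined protocol and SAP*

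**What the plan says.** - **Model.** Section 8.1.4.2.1 analyses each co-primary endpoint (DYS and NMPP response at Month 6, Group C against Group B) with a "logistic regression model including treatment as the main factor and baseline pain score as a covariate". No other covariate is named.
- **Baseline.** Section 8.1.3 defines it, unless noted otherwise, as the "last value obtained prior to the first dose of the study drug during the Open-label Run-in Period". For the NRS, Section 5.5.3 uses the mean over the 35 days before first dose.
- **Randomization.** Section 5.5.3 says that Month 3 incomplete responders on the NRS "will be assigned randomly (in an equal ratio) via IRT in a blinded manner to either Treatment Group B or Treatment Group C". No stratification is described.
- **Diary.** Under Section 5.1, "Subjects will continue to use the daily e-Diary to record DYS, NMPP; dyspareunia" and the other diary items through Month 6. It also sends to Group A, unrandomized, "any subjects that have zero entries for the Daily Diary for endometriosis-associated pain score via NRS during the 35 day window" before the Month 3 visit.
- **Analysis set.** Section 8.1.2: "all subjects who receive at least 1 dose of study drug during the Double-blind Period will be included in the Double-blind full analyses".
- **Response.** The criterion "will include a reduction of X or greater from baseline in the average pain score as well as no increased analgesic rescue use". If no period is reported in the 35-day window, "then mean score for DYS for that time point will be set equal to zero".

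Section 8.1.4.1 leaves analysis details to a SAP whose text is not in the file, so this point concerns the model as the protocol states it.

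**The concern.** The covariate is measured before the open-label run-in, but randomization happens after it. With 28-day months the gap is 3 x 28 = 84 days, during which every subject takes elagolix 150 mg QD. By the Month 3 visit each subject has a 35-day DYS and NMPP record that precedes randomization, so it is a legitimate covariate. It is also closer in time to the outcome than the pre-dose score.

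What is at stake is precision in estimating the benefit of escalation, and some power if the true effect is well below the one assumed. Validity is not at stake. The Month 3 score is balanced between B and C in expectation, so omitting it biases neither the test nor the difference in response rates.

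**Working it through.** **1. The plan's own figure.** Section 8.3 assumes 20% (B) v 50% (C), two-sided alpha 0.05, and claims more than 90% power. For 90% power:

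n per arm = [1.96 x sqrt(2 x 0.35 x 0.65) + 1.2816 x sqrt(0.2 x 0.8 + 0.5 x 0.5)]^2 / 0.30^2 = (1.322 + 0.821)^2 / 0.09 = 51.0, so 52 (58 with continuity correction).

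With no loss before Month 3 there are 890 x 0.5 / 2 = 222 per arm and power exceeds 99.99%. With 50% loss (111 per arm) it is 99.8%. The claim holds comfortably.

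**2. Arm size used here.** Section 8.3 gives 25% completion at 24 months and no Month 3 figure. Assuming constant-hazard dropout, 0.25^(3/24) = 0.841 remain at Month 3, so 890 x 0.841 / 4 = 187 per arm.

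**3. Simulation set-up.** The documents give no correlations between pain scores, so all of these are assumptions:
- Trivariate normal scores: baseline-Month 3 correlation 0.6, baseline-Month 6 0.5, Month 3-Month 6 r = 0.5, 0.7 or 0.8.
- The half with less improvement on an NRS proxy (correlation 0.8 with the baseline-to-Month 3 change) is randomized 1:1.
- Response is a reduction from baseline beyond X with no rescue failure; rescue failure is independent, at 0, 10, 20 or 30%.
- The logistic model has treatment and baseline, with or without the Month 3 score; Wald test; g-computed risk difference with delta-method SE.
- 10,000 trials per scenario at 20% v 33% and 20% v 20%; 5,000 at 20% v 50%. The 33% is an illustrative smaller effect, not a figure from the plan.

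**4. Results at 20% v 33%.** The first two result columns cover 0-30% rescue failure. The 95% CI half-width is at 10% rescue failure, in percentage points.

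| r | Fall in risk-difference variance | Power gain (from 0.84-0.87) | 95% CI half-width | SE of log OR | Odds ratio |
|---|---|---|---|---|---|
| 0.5 | 1-2% | up to 0.01 | 8.4 to 8.3 | 0.256 to 0.261 | 2.1 to 2.2 |
| 0.7 | 7-12% | 0.03-0.04 | 8.4 to 7.9 | 0.256 to 0.275 | 2.1 to 2.4 |
| 0.8 | 12-22% | 0.05-0.07 | 8.4 to 7.5 | 0.256 to 0.291 | 2.1 to 2.6 |

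The half-widths agree with the variance column: 1 - (7.9/8.4)^2 = 12% and 1 - (7.5/8.4)^2 = 20%.

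The log odds ratio SE rises, yet the test gains, because the conditional log odds ratio rises faster. At r = 0.7, using the rounded figures, ln(2.1)/0.256 = 2.9 becomes ln(2.4)/0.275 = 3.2.

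**5. Planned effect and null.** At 20% v 50%, power is 1.00 either way and the half-width goes from 8.7 points to 8.6, 8.3 or 7.9. At 20% v 20%, type I error is 0.047-0.052 with the covariate and 0.048-0.052 without.

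**6. DYS zeros.** Assume 10% have no period at Month 3 (score 0, set 4 SD below the mean), with no period at Month 6 in 50% of those and 5% of the others, and 10% rescue failure (6,000 trials). For r = 0.5, 0.7 and 0.8 the variance falls by 6%, 8% and 10% with a linear term, and by 6%, 8% and 13% with a no-period indicator added.

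**7. Robustness.** A separately coded run used 222 per arm, no rescue component, lower baseline correlations and r from 0.4 to 0.8 (1,500 trials per scenario). At 20% v 30%, power rose from 0.73-0.78 to 0.81-0.86. The mean risk difference was unchanged by the covariate: 0.10 at 20% v 30% and 0.30 at 20% v 50%.

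**The case against.** The strongest reply is that no defect is alleged. The model adjusts for the score from which response is computed, which is coherent, and at the plan's own 20% v 50% the extra covariate does nothing for power. That is right, and it is why this ranks as optional.

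The size of the gain is also open to challenge:
- **One correlation for both arms.** Group C changes regimen at Month 3, so its Month 3 score may predict Month 6 less well. At 20% v 33% with r = 0.7 in B and 0.4 in C (baseline-Month 6 0.3 in C), the variance reduction falls to 6% and the power gain to 0.02. With 0.5 in B and 0.3 in C they are 1% and under 0.01. This stands; the benefit could be close to nil.
- **DYS.** The check in step 6 ties no period at Month 6 to no period at Month 3. If it is instead 20% in C and 5% in B, unrelated to Month 3, the reduction at r = 0.7 is 5%, or 2% with the weaker Group C correlation. This stands too: the 7-22% range at r = 0.7-0.8 should not be read as covering DYS.
- **Arm size.** The plan's figure of at least 120 subjects on 150 mg QD for 24 months reproduces as (445 + 44.5) x 0.25 = 122 with no separate loss before Month 3, which implies 222 per arm. Power at 20% v 33% with baseline alone is then already 0.90, leaving less to gain.
- **Effect measure.** The tighter interval appears in a risk difference the protocol does not specify, and the odds ratio becomes conditional on two scores. This is correct and belongs to the cost.

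None of this removes the point. The covariate is already collected, precedes randomization and does no harm to validity.

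**Conclusion.** The point holds as an optional refinement. The stated model uses only the pre-dose score although a Month 3 score is available at randomization. The omission causes no bias and no type I inflation, and has no practical effect on power at 20% v 50%.

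The plausible reduction in risk-difference variance runs from about 1% to 22%. Single-digit values are likely if Group C's scores decouple from Month 3, or for DYS where having no period is not persistent. Power matters only if the true effect is clearly smaller than planned; the gain is then from under 0.01 to about 0.07 at 20% v 33%.

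The direction is secure. The size rests on assumed correlations, normal scores, independent rescue failure and 187 per arm, so confidence in it is medium.

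**What to change.** In Section 8.1.4.2.1, before unblinding:

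1. Add to each model the mean of the same scale over the 35 days before the Month 3 visit (DYS in the DYS model, NMPP in the NMPP model), alongside pre-dose baseline. Do the same in the percent-change repeat.
2. Leave the responder definition unchanged.
3. Report with the odds ratio a standardized (g-computed) risk difference, C minus B, with its 95% CI, and state that the odds ratio is conditional on both scores.
4. State that the no-period rule (DYS set to zero) also applies at Month 3, and add a no-period indicator if zeros are common.
5. For a randomized subject with no usable Month 3 entry on a scale, use the mean pooled over both arms plus a missing indicator.

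The cost is low but not zero. No new data are needed, but the SAP must define the Month 3 window, the zero rule, a sparse-diary rule and the risk-difference estimator, and the odds ratio will differ from one adjusted for baseline alone. Wholly empty Month 3 diaries should be rare in B and C because subjects with no NRS entries go to Group A. That rule concerns the NRS only and does not guarantee DYS or NMPP entries, so item 5 is still needed.
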